#### 7.6.11 Physical Examinations

Physical examination findings will be presented in a subject listing.

### 7.6.12 ECOG

ECOG performance status will be summarized categorically (ECOG grade: 1, 2, 3, and 4) for each scheduled study visit. Shift tables showing baseline ECOG grade and maximum grade on treatment will be provided. The on-treatment period starts at first dose and ends at 100 days after last study therapy.

A by-subject listing of ECOG will also be provided. Classification of ECOG performance status is provided below.

Performance Status Criteria		
Fully active, able to earry on all pre-disease activities without restriction.		
Restricted in physically strenuous activity but ambulatory and able to carry out work of a light sedentary nature (light housework, office work).		
Ambulatory and capable of all self-care but unable to carry out any work activities. Up and about more than 50% of waking hours.		
Capable of only limited self-care, confined to bed or chair more than 50% of waking hours.		
Completely disabled. Cannot carry on any self-care. Totally confined to bed or chair.		

#### 7.6.13 Pregnancy Testing

A listing of pregnancy tests results will be provided for all treated female subjects.

#### 7.7 Pharmacokinetics

#### 7.7.1 Serum cabiralizumab and nivolumab Concentration

Individual and mean serum concentration of cabiralizumab and nivolumab versus time data will be plotted by individual or combined cohort with different dose and regimen. Summary statistics will be tabulated for the serum concentration-time data of cabiralizumab and nivolumab, as appropriate. For the purpose of calculating or plotting mean concentration-time data, below the lower limit of assay quantitation (LLOQ) values will be treated as missing.

#### 7.7.2 **PK Parameters**

The PK evaluable population will be used for all summaries of the PK parameters. Summary statistics will be tabulated for each PK parameter by individual or combined cohort with different dose and regimen. Geometric means and coefficients of variation will be presented for Cmax, AUC(0-T), AUC(TAU), Cmin, Ctrough, CL, Vss, MRT and AIs. Medians and ranges (minimum and maximum) will be presented for Tmax. Means and standard deviations will be presented for other PK parameters (i.e., t1/2).

Pharmacokinetic parameters of cabiralizumab will be derived from the serum concentration versus time profiles for the intensively sampled Cycle 1, Day 1 and Cycle 8, Day 1 dose administration in both Phase 1a and Phase 1b of the study. Individual PK parameter values will be derived by non-compartmental methods by a validated PK analysis program using actual times.

Parameter	Units	Definition
Cmax	µg/mL	Maximum observed serum concentration
Tmax	h	Time of maximum observed serum concentration
AUC(0-T)	μg.d/mL	Area under the serum concentration-time curve from time zero to time of last quantifiable concentration
AUC(TAU)	µg.d/mL	Area under the serum concentration-time curve in one dosing interval
Cmin	µg/mL	Minimum observed serum concentration during a dosing interval (excludes pre-dose concentration before the first dose)
Ctrough	µg/mL	Concentration associated with the sample at the end of each dose interval.
CL	L/d	Total body clearance calculated Dose divided by AUC(TAU) for Cycle 8, Day 1
AI_AUC	-	AUC accumulation index; ratio of AUC(TAU) for Cycle 8, Day 1 to AUC(TAU) after the first dose
AI_Cmax	-	Cmax accumulation index; ratio of Cmax from any cycles to Cmax after the first dose
AI_Cmin	-	Cmin accumulation index; ratio of Cmin for Cycle 8, Day 1 to Cmin after the first dose
AI_Ctrough	-	Ctough accumulation index; ratio of Ctrough from any cycles to Ctrough after the first dose
pAUCe	%	Percent of AUC extrapolated from the last quantifiable concentration to infinity (Cycle 1, Day 1 only)
λz	d-1	Slope of terminal log-linear elimination phase
Adj R 	-	Adjusted R  of terminal elimination phase
Lz_Start	d	The time point starting the log-linear elimination phase defining the terminal half-life
Lz_End	d	The time point ending the log-linear elimination phase defining the terminal half-life

Parameter	Units	Definition			
Lz_N	-	Number of time points in the log-linear elimination phase defining the terminal half-life			
MRT	d	Mean residence time. MRT = (AUMCinf/AUCinf) – T/2 where AUMCinf=Area under moments curve of the serum concentration- time from time 0 to infinity, AUCinf=Area under the serum concentration-time curve from time 0 to infinity, and T= infusion duration			
t1/2	d	Terminal half-life calculated post first dose. $t1/2=ln(2)/\lambda z$			
Vss	mL/kg	Steady-state distribution volume projected post first dose. Vss= CL*MRT.			

Dose-normalized values for AUCs, Cmax, Cmin, and Ctrough will also be presented using the actual dose administered.

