### 5.3.3 Pharmacokinetic Assessments

Blood samples for the PK evaluation of both cabiralizumab and nivolumab will be collected from all patients.

Patients enrolled in Phase 1a and Phase 1b will have blood drawn for measurement of serum cabiralizumab concentration. Blood samples will be collected during Cycle 1 and Cycle 8 on Days 1, 2, 4, and 8 as well as both before and after infusion for Cycle 2, 3 and 4. In addition, blood samples will be collected before the infusion on Cycles 5, 9, 13, and 21, then every 6 cycles while on treatment. A blood sample will also be collected for PK analysis during the End-of-Treatment Follow-up Period (28 [±7] days and 100 [±7] days post-last dose).

Patients enrolled in the 3-week dosing regimen cohort (1aD) will have additional blood sample drawn on Day 15 of Cycles 1 and 8. See Appendix C for specific collection time points.

Patients enrolled in Phase 1a and Phase 1b combination cohorts will have blood drawn for measurement of serum nivolumab concentration. Blood samples will be collected both before and at the end of infusion for Cycle 1 to Cycle 4. In addition, blood samples will be collected at the end of the infusion for Cycle 8 and before the infusion on Cycles 5, 9, 13, and 21. A blood sample will also be collected during the End-of-Treatment Follow-up Period.

Standard PK parameters will be determined based on serum cabiralizumab concentration-time data, as appropriate. Nivolumab accumulation will be evaluated as appropriate.

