#### **6.5 Pregnancy**

If, following initiation of the investigational product, it is discovered that a study patient is pregnant or may have been pregnant at the time of investigational product exposure, including during at least 5 half-lives (90 days) after product administration, the investigational product will be permanently discontinued in an appropriate manner.

The Investigator must immediately notify the Sponsor's (or designee's) Medical Monitor of this event and complete and forward a Pregnancy Form to the Sponsor (or designee) within 24 hours and in accordance with SAE reporting procedures described in Section 6.2.1.

Follow-up information regarding the course of the pregnancy, including perinatal and neonatal outcome and, where applicable, offspring information, must be reported on the Pregnancy Surveillance Form.

Any pregnancy that occurs in a female partner of a male study participant should be reported to the Sponsor. Information on this pregnancy will be collected on the Pregnancy Surveillance Form.

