### 7.7.4.2 PK Parameter Evaluation

For cabiralizumab, PK parameters including Cmax, AUC, Cmin, Ctrough, CL, Vss, and MRT will be estimated. The cabiralizumab accumulation ratio for Cmax, Cmin, and Ctrough, and AUC will be estimated for different cycles, as data permit. For nivolumab, Ctrough will be reported and accumulation will be evaluated for different cycles, as data permit.

Dose-proportionality will be assessed based on available cabiralizumab PK parameters if applicable.

Only data points that describe the terminal elimination log-linear decline will be used in the regression equation for calculation of  $\lambda_z$ .  $C_{max}$  and any data point in the distribution phase will not be included in the calculation of  $\lambda_z$ . A minimum of 3 points will be used for determination of the terminal elimination phase rate constant. A value of adjusted  $r^2 > 0.80$  will be considered acceptable for the calculation of the terminal elimination phase rate constant. If adjusted  $r^2$  falls below 0.80, or the above conditions are not met, then the terminal elimination phase rate constant and the associated values of t1/2, AUC(INF), CL and Vss will be flagged. If pAUCe is more than 20%, then AUC(INF) and CL will be flagged. Flagged values will not be included in the calculation of descriptive statistics.

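### SAP 7.7.2 and 7.7.4.2 do not agree on CL, MRT and Vss: the dosing occasions, the exclusion flags and the units conflict

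*SAP*

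**What the plan says.** SAP 7.7.2 takes cabiralizumab parameters by noncompartmental analysis, "derived from the serum concentration versus time profiles for the intensively sampled Cycle 1, Day 1 and Cycle 8, Day 1 dose administration". Its table then gives:

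- CL, in L/d: "Total body clearance calculated Dose divided by AUC(TAU) for Cycle 8, Day 1". No other CL is defined.
- MRT, in days: AUMCinf/AUCinf minus half the infusion time, with "AUCinf=Area under the serum concentration-time curve from time 0 to infinity". No occasion is given.
- t1/2: "Terminal half-life calculated post first dose".
- Vss, in mL/kg: "Steady-state distribution volume projected post first dose. Vss= CL*MRT".
- pAUCe, the extrapolated percentage of AUC: Cycle 1 Day 1 only.

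SAP 7.7.4.2 has two exclusion rules. The first concerns fit: if adjusted r² falls below 0.80, or the conditions for the terminal slope λz are not met, then λz, t1/2, AUC(INF), CL and Vss are flagged. The second concerns extrapolation: "If pAUCe is more than 20%, then AUC(INF) and CL will be flagged". Flagged values are left out of the descriptive statistics. SAP 7.7.2 summarises CL, Vss and MRT by geometric mean and coefficient of variation. CL and Vss are named secondary PK endpoints in both phases (Protocol 7.3.1.2 and 7.3.2.2; SAP 4.2).

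**The concern.** A programmer who follows the table as written builds a first-dose volume from a Cycle 8 clearance. If clearance changes over those cycles, Vss moves by the same proportion with no change in volume. Patients who stop before Cycle 8 have no Vss at all.

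The extrapolation rule also names the wrong parameters. It spares MRT, which rests on two areas to infinity, and Vss, which is built on MRT. It removes a clearance that rests on one observed dosing interval. A patient's CL can therefore be excluded as unreliable while the Vss calculated from that same CL stays in the table.

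**Working it through.** The documents give no PK result or planning figure on this point, so there is nothing to reproduce first.

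**Inputs.** Sampling after the first dose is on Days 1, 2, 4 and 8 (also Day 15 in cohort 1aD). It ends with the pre-dose sample of Cycle 2, about T = 14 days after dosing, or 21 days in 1aD (Protocol 5.3.3 and Appendix C). No half-life for cabiralizumab is stated. The only indirect figure is in Protocol 6.5, "including during at least 5 half-lives (90 days) after product administration", which gives 90/5 = 18 days. That text does not say which product it describes, so 18 days is an assumption and a range is shown.

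**1. Occasions.** Cycle 8 Day 1 falls on day 7 × 14 + 1 = 99, or 7 × 21 + 1 = 148 in 1aD. That MRT is a first-dose value is inferred from the Vss and t1/2 rows and from pAUCe being Cycle 1 only. Taking MRT at Cycle 8 would not help. Areas to infinity from a Cycle 8 profile include drug from earlier doses, so AUMCinf/AUCinf is not in general the residence time there.

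**2. Size of the mixing error.** Vss as written / Vss from the first dose alone = CL(Cycle 8)/CL(Cycle 1).

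- Ratio 0.8: Vss is 20% too low. Ratio 1.25: 25% too high.
- Constant clearance, 18-day half-life, dosing every 2 weeks: AUC(TAU) at dose 8 is 1 − exp(−ln2 × 112/18) = 0.987 of AUCinf, so the error is about 1%.

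**3. Extrapolated share after the first dose.** Assume mono-exponential decline and let x = ln2 × T/t1/2. The AUC share is exp(−x). The AUMC share is exp(−x)(1 + x), which is larger for every x > 0.

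| Half-life | AUC / AUMC, T = 14 d | AUC / AUMC, T = 21 d |
|---|---|---|
| 3 d | 4% / 17% | 1% / 5% |
| 6 d | 20% / 52% | 9% / 30% |
| 10 d | 38% / 75% | 23% / 57% |
| 18 d | 58% / 90% | 45% / 81% |
| 25 d | 68% / 94% | 56% / 88% |

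pAUCe reaches 20% at t1/2 = T × ln2/ln5, which is 6.0 d (14-day window) or 9.0 d (21-day window). AUMC is more than half extrapolated once t1/2 exceeds 5.8 d or 8.7 d respectively. With a bi-exponential curve (assumed fast half-life 1.5 d carrying 10% to 30% of AUC), the 18-day, 14-day-window figures become 53% to 41% for AUC and 89% to 87% for AUMC.

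Sensitivity at 18 d with T = 14 d: the true MRT is 18/ln2 = 26.0 d. Underestimating λz by 20% gives 31.9 d (+23%). Overestimating it by 20% gives 22.1 d (−15%).

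**4. What each rule covers.**

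| Parameter | Needs extrapolation? | Fit rule | pAUCe > 20% rule |
|---|---|---|---|
| AUC(INF) | Yes | Yes | Yes |
| CL, Cycle 8, Dose/AUC(TAU) | No | Yes | Yes |
| MRT | Yes | No | No |
| Vss = CL × MRT | Through MRT | Yes | No |

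The fit rule cannot stand in for the extrapolation rule. An error-free mono-exponential curve with an 18-day half-life has r² = 1 and still has 58% of its AUC extrapolated.

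**5. Units.** L/d × d = L. To reach mL/kg, CL must be formed from dose per kg.

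**The case against.** The strongest reply is that the authors meant something coherent. Section 7.7.4.2 ties CL to λz and to AUC(INF), and pAUCe exists only for Cycle 1. Both fit an intended first-dose CL = Dose/AUC(INF), hence a single-occasion Vss, with the CL row simply incomplete. That is plausible, and on that reading Vss would not depend on reaching Cycle 8. But the table says otherwise, so the two sections need reconciling in any case, and MRT and Vss would still escape the extrapolation rule.

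A reader might go further and infer that the reported MRT and Vss are both mostly extrapolation and both mix two occasions. The documents do not support that:

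- MRT comes from one profile and mixes nothing. Only Vss does, and its CL factor, as defined, is observed.
- AUMC is mostly extrapolated only above about 5.8 d (14-day window) or 8.7 d (21-day window). The 18 days comes from pregnancy text, and both drugs are investigational products (Protocol 4.1).
- Vss is not unprotected: the fit rule covers it, though not MRT.

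It is also fair that all analyses are descriptive (Protocol 7), that no decision rule uses Vss, that nothing in the documents shows clearance changing, and that the SAP provides for independent PK review. These points limit the consequence. They do not remove the conflict in the text.

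**Conclusion.** The SAP is wrong as written on a named secondary endpoint. Four conflicts hold without any assumed half-life: Vss pairs a Cycle 8 CL with a volume labelled as first-dose; the 20% rule omits MRT and Vss; it removes a CL that involves no extrapolation while keeping the Vss built from it; and the units do not match.

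The numerical effect is conditional. The mixing error is about 1% with constant clearance and an 18-day half-life, and otherwise unknown. The extrapolated shares depend on half-life and, as tabulated, on mono-exponential decline. At 18 days with two-weekly dosing nearly every patient would exceed 20%, so the CL summary could be almost empty while MRT and Vss remained in full. Below about 6 days (9 days in 1aD) the 20% rule would seldom act.

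**What to change.** Amend SAP 7.7.2 and 7.7.4.2:

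1. State that MRT is taken after the first dose. Define a separate first-dose CL = Dose/AUC(INF), with dose per kg, and set Vss = first-dose CL × MRT, in mL/kg.
2. Apply the pAUCe > 20% flag to AUC(INF), first-dose CL, MRT and Vss. Do not apply it to Cycle 8 CL = Dose/AUC(TAU).
3. Add MRT to the adjusted r²/λz flag and remove Cycle 8 CL from it.

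This is wording only and needs no new samples. The price is that few noncompartmental MRT and Vss values may survive if the half-life is long. The population or compartmental analysis that SAP 7.7.4.1 already allows is then an option, not a requirement. It could use the later samples (Protocol 5.3.3: "A blood sample will also be collected for PK analysis during the End-of-Treatment Follow-up Period", at 28 and 100 days after the last dose), which cannot shorten the first-dose extrapolation. It has its own cost: Protocol 7.4.4 places population PK modelling in a separate report.

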#### 7.7.3 Quality Control Methods for PK Data Analysis

The PK analysis will be subject to Quality Control (QC) review and also review by an independent pharmacokinetist at ICON.

#### 7.7.4 Pharmacokinetic Assessments

### 7.7.4.1 PK analysis Software

Pharmacokinetic (PK) parameters will be calculated from the serum drug concentration-time data and actual elapsed sampling time using a non-compartmental analysis (NCA) method with i.v infusion input in Phoenix WinNonLin (Build 8.0.0.3176 or higher, Certara LP, St. Louis, MO). Alternative PK analysis methods may be considered if necessary, for example, a population PK analysis or compartmental modeling. Data summaries and plots will be produced using SAS Version 9.1 or higher (SAS Institute, Cary, NC).

### 7.7.4.2 PK Parameter Evaluation

For cabiralizumab, PK parameters including Cmax, AUC, Cmin, Ctrough, CL, Vss, and MRT will be estimated. The cabiralizumab accumulation ratio for Cmax, Cmin, and Ctrough, and AUC will be estimated for different cycles, as data permit. For nivolumab, Ctrough will be reported and accumulation will be evaluated for different cycles, as data permit.

Dose-proportionality will be assessed based on available cabiralizumab PK parameters if applicable.

Only data points that describe the terminal elimination log-linear decline will be used in the regression equation for calculation of  $\lambda_z$ .  $C_{max}$  and any data point in the distribution phase will not be included in the calculation of  $\lambda_z$ . A minimum of 3 points will be used for determination of the terminal elimination phase rate constant. A value of adjusted  $r^2 > 0.80$  will be considered acceptable for the calculation of the terminal elimination phase rate constant. If adjusted  $r^2$  falls below 0.80, or the above conditions are not met, then the terminal elimination phase rate constant and the associated values of t1/2, AUC(INF), CL and Vss will be flagged. If pAUCe is more than 20%, then AUC(INF) and CL will be flagged. Flagged values will not be included in the calculation of descriptive statistics.

#### 7.7.4.3 Treatment of Outliers

Individual serum concentration-time points, if considered anomalous, may be excluded from the analysis at the discretion of the pharmacokineticist following a review of the available documentation. Any such exclusion will be discussed with the Sponsor's Clinical Pharmacologist and clearly outlined in the CSR.

Entire individual treatment profiles for a subject may be excluded following review of the available documentation and discussion with the Sponsor. However, results of analysis with and without the excluded profiles may be presented in the CSR. Any such exclusion will be clearly listed in the CSR along with justification for exclusion.

Any anomalous concentration values observed prior to the first dose will be identified and discussed in the CSR.

#### 7.7.4.4 Non-Quantifiable or LLOQ Concentrations

For the calculation of PK parameters, predose concentration values prior to the first quantifiable concentration that are below LLOQ values will be assigned a value of zero and thereafter any LLOQ values will be set to missing.

### 7.9 Conventions

### 7.9.1 Decimal Places

The number of decimal places displayed in all listings will be determined by the number of decimal places in the raw data.

Unless otherwise specified, minimum and maximum will be reported to the precision as the data collected, one more decimal place for the mean and median, and two more decimal places for the standard deviation. Percentages will be reported with one decimal point.

## 7.9.1.1 Missing data

No imputation of values for other missing data will be performed, unless specified,

### Adverse Event:

If due to partial dates or times, it is not possible to definitively conclude that an AE is not treatment emergent, then a conservative approach will be taken into account whereby it will be classified as a TEAE, e.g. if the first dose date is "10June" and the AE starts in "June", then that AE will be classified as a TEAE, unless the AE stop date precludes this (i.e. the AE stop date is definitively prior to the first dose date).

Imputation rules for missing or partial AE start date are defined below:

### If only Day of AE start date is missing:

If the AE start year and month are the same as that for the first dose date, then:

- If the full (or partial) AE end date is NOT before the first dose date or AE end date is missing, then impute the AE start day as the day of first dose date; otherwise, impute the AE start day as 1.
- Otherwise, impute the AE start day as 1.

Compare the imputed AE start date with TE period to determine whether the AE is pretreatment AE, TEAE or post-treatment AE.

### If Day and Month of AE start date are missing:

If AE start year = first dose year, then:

- If the full (or partial) AE end date is NOT before the first dose date or AE end date is missing, then impute the AE start Month and Day as the Month and Day of first dose date; otherwise, impute the AE start Month as January and the Day as 1.
- Otherwise, impute the AE start MONTH as January and the DAY as 1.

Compare the imputed AE start date with TE period to determine whether the AE is pretreatment AE, TEAE or post-treatment AE.

### If Year of AE start date is missing:

If the year of AE start is missing or AE start date is completely missing then query site with no imputation. Also compare the full (or partial) AE end date to the first dose date. If the AE end date is before the first dose date then the AE should be considered as a pretreatment AE. Otherwise, the AE will be considered as TEAE.

·	Summary of Changes						
Version	Summary of Changes						
1.0	Original version						
2.0	
 
Added that PK analyses will be presented by individual or combined cohort by different dose and regimen
 
						
	• Removed PFS, ORR, and DOR analysis for colon rectum cancer						
	• Corrected '1aD' to '1aD1' in calculation of exposure and relative dose intensity						
	Removed Screened Population from the analysis						
• Changed window of concomitant medication from 10 to 100 days after last dose of any study drug (or until subsequent anticancer therapy in long-term follow-up							
	• Italicized 'and' / 'or' in the concurrent hepatica abnormality criteria for clarification						
	Changed immunogenicity on-treatment period						
	• Added baseline nivolumab ADA-negative and baseline cabiralizumab ADA-negative in immunogenicity summary						
	• Changed subgroup summary of trough concentration of cabiralizumab and nivolumab from by baseline ADA status to by postbaseline ADA status						
	• Reference of 'CLT' was changed to 'CL" in SAP text						
	• Reference of 'T HALF' was changed to 't1/2' in SAP text						
	• Added definition for MRT, t1/2, and Vss.						
• Updated version of Phoenix WinNonLin							
	Clarified MedDRA version						

### 8 **DOCUMENT HISTORY**

## 9 **REFERENCES**

#### 10 APPENDIX

#### **APPENDIX 1: Major changes to stats analysis in protocol amendments**

- I. Protocol Version 2 Amendment 1, 14 July 2015 None.
- II. Protocol Version 3 Amendment 2, 02 October 2015
  - 1. Changed the definition of "Enrolled Population" as "All patients who sign the ICF and are approved for enrollment by sponsor or designee, and for Phase 1b patients only, are registered in IXRS"
  - 2. Added new analysis population "Evaluable Population: Patients who have a measureable lesion at baseline and have at least 1 post-baseline tumor assessment."
  - 3. Section 7.4.2 Efficacy analysis, the definition of Overall Response Rate (ORR) is updated as "defined as the ratio of the number of patients that achieve an objective response to total number of patients who are evaluable for a response."
  - 4. Changed dosing for the : Cohort 1aM2: FPA008 6 mg/kg every 2 weeks
  - 5. Clarified ORR is defined as the ratio of the number of patients that achieve an objective response to total number of patients who are evaluable for a response
- III. Protocol Version 4 Amendment 3, 15 April 2016
  - Updated Sample size for the study as "Approximately 70 patients will be enrolled in Phase 1a (dose escalation); between 3 and 9 patients are expected to be treated at each dose escalation cohort according to the algorithm outlined in Table 4 (refer protocol). There will also be up to 40 patients enrolled into completed cohorts to further explore safety, PK, and PD."
- IV. Protocol Version 5 Amendment 4, 07 June 2017
  - 1. Updated investigational product FPA008 to cabiralizumab
  - 2. Updated total number of patients for the study
  - 3. Clarified adverse event and concomitant medications follow up period
  - 4. Updated evaluable population for analyses
  - 5. Revised Pharmacodynamic Biomarkers and Immunogenicity endpoints
  - 6. Specified efficacy assessment is based of RECIST v1.1 by investigator assessment
  - 7. Added efficacy assessment by Independent Radiology Review and exploratory end point in Phase 1b
  - 8. Defined objective response and clarified parameter for safety analyses
  - 9. Removed electronic SAE form and Pregnancy Surveillance form

APPENDIX	2:	Baseline	Disease	Characteristics
----------	----	----------	---------	-----------------

	MELANOMA	NSCLC	OVARIAN	SCCHN	PANCREATIC	RCC	GBM
Baseline Disease			Cancer		Cancer		
Characteristics							
DISEASE STAGE AT	×	×	×	×	×	×	×
DIAGNOSIS							
SITEOFMETASTATIC	×	×	×	×	×	×	×
DISEASE							
PRIORSURGERY	×	×	×	×	×	×	×
PRIORRADIATION	×	×	×	×	×	×	×
PRIOR SYSTEIVIC	Â	Ŷ	Î Î	^	^	Ŷ	Ŷ
PD-L1STATUS	×	×	×	×	×	×	×
TOBACCOUSE	×	×	×	×	×	×	×
M STAGE AT STUDY ENTRY	×						
BRAF STATUS	×						
BASELINEBRAIN METASTATSIS	×	×					
BASELINE LDH	×					×	
ALK STATUS		×					
EGFR STATUS		×					
KRAS STATUS		×					
CELL TYPE		×				×	
BRCA STATUS			×				
HPV STATUS				×			
				×			

